Aim 3 individual in-depth interviews. We will conduct 20-30 patient interviews and approximately 10 provider interviews in each state.

Sampling Method

Aims 1 & 2. Consecutive sampling. The entire eligible one-year cohort will be used for analyses based on administrative data, and consecutive sampling will be used to enroll survey participants from that cohort until target enrollment numbers are reached.

Aim 3 key informants. Purposive and snowball sampling. Potential key informants will be identified and invited to participate based on specific characteristics. Snowball sampling from these initial interviews will allow us to expand the sample until the body of interview data achieves theoretical saturation in each state.

Aim 3 individual in-depth interviews. Purposive and quota sampling. Potential interview participants will be identified and invited to participate based on specified characteristics until the body of interview data achieves theoretical saturation in each state. For provider interviews, we will also ask interviewed providers to recommend peers with experience prescribing opioids for WC patients (snowball sampling).

5. Exposures

The primary exposures of interest are the WC-based opioid review programs (ORPs) in each state: (1) prospective prior authorization (PA) with hard stops in WA, and (2) retrospective review (RR) with prescriber notification in OH. Secondarily, the COHE program is an exposure of interest, within WA only.

WA opioid review. Under WA regulatory procedures, payment for any opioid prescription billed beyond six weeks after the injury is denied unless the prescriber has submitted a checklist attesting to completion of all best practices from the regulations/guidelines. For example, the provider must document clinically meaningful improvement in pain and function during acute use. Thus, the WA intervention is prospective and includes a “hard stop” subject to an insurer’s decision based on regulatory authority.

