OH opioid review. The OH regulations are similar to those in WA regarding best practices, but differ in approach. Rather than a “hard stop” on opioid prescription payments, an automated report identifies new opioid prescriptions beyond the acute phase. OH WC pharmacy and clinical staff review the medical record at 12 weeks to determine whether best practices were met. If not, the prescriber is notified via letter, and cases are reviewed again at 16 weeks. If best practices have still not been met, the prescriber

and worker are notified via letter that opioid coverage will end in 4 weeks. The OH program relies on retrospective chart review and communication of best practices to prescribers.

Centers of Occupational Health and Education (COHE) care delivery, in WA. The focus of the COHEs is to deliver occupational health best practices during the first 12 weeks after injury, during the transition from acute/subacute to chronic pain. The COHE delivery system has been developed over the past decade, and now approximately 50% of workers in WA receive care under these innovative arrangements. Critical elements of the COHE model include organizing care delivery on a population basis, high level executive health system support, ongoing care coordination by health service coordinators (HSCs), and stepped care management. Specific best practices include screening for psychosocial barriers to recovery using the validated Functional Recovery Questionnaire (FRQ); initiation of graded exercise; education regarding psychosocial barriers to recovery; and, more recently, a brief series of cognitive behavioral and reactivation techniques, i.e., activity coaching. COHE is a health care systems intervention, rather than a specific health care service or menu of services, that is primarily focused on improving the coordination of care at the health care community level, as well as with DLI. The COHE model consists of enhanced provider education regarding occupational health best practices and stepped-care features. Both usual care and COHE-based care in the WA workers' compensation (WC) system include the typical mix of health care services delivered for work-related injuries in Washington State, such as chiropractic care, physical therapy, evidence-based imaging services, and guideline-concordant surgery.

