Enhanced Care Program (ECP), in OH. Although OH has no program entirely comparable to COHE, the OH BWC did initiate the ECP as a pilot program in 2016, to assess the effect of improving care coordination and treatment planning for injured workers with knee sprains. The pilot was established in selected counties in northeast Ohio. Providers participate on a voluntary basis and agree to use a new treatment planning form for injured workers with knee sprains and to coordinate care for those needing referral for physical therapy or specialty care. Participating providers receive 15% added payment for evaluation and management visits. The pilot is being extended during the next two years throughout OH but will remain limited to injured workers with knee sprains.

6. Outcomes

The primary outcome measure, unsafe opioid prescribing, will be measured as shown in Table 1 using pharmacy billing data from OH and WA, and validated using state PDMP data. Table 2 presents secondary outcome measures, and Table 3 presents exploratory/other outcome measures.

Table 1. Primary Outcome Measures		
Title	Description	Timeframe (after injury)
Unsafe opioid prescribing (subacute phase): Days supply	>7 days supply	6-12 weeks
Unsafe opioid prescribing (chronic phase): Chronic	≥60 days supply	3-6, 6-9, and 9-12 months
Unsafe opioid prescribing (chronic phase): Concurrent	Concurrent sedatives/hypnotics	3-6, 6-9, and 9-12 months
Unsafe opioid prescribing (chronic phase): High dose	≥50 MED/day	3-6, 6-9, and 9-12 months
Unsafe opioid prescribing (chronic phase): Composite	Meeting ≥1 of the 3 chronic-phase metrics	3-6, 6-9, and 9-12 months

MED, morphine equivalent dose.

Table 2. Secondary Outcome Measures

Title	Data Source	Description	Timeframe (after injury)
Pain intensity	Survey	PEG-3 Scale	6 weeks, 6 months, 12 months
Physical function/pain interference	Survey	PEG-3 Scale	6 weeks, 6 months, 12 months
Emotional functioning-Anxiety	Survey	PHQ-4 (Patient Health Questionnaire for anxiety and depression)	6 weeks, 6 months, 12 months
Emotional functioning-Mood	Survey	PHQ-4 (Patient Health Questionnaire for anxiety and depression)	6 weeks, 6 months, 12 months
Global improvement	Survey	Patient Global Impression of Change scale	6 months, 12 months
Disability	Survey	Does health now limit activities during a typical day	6 months, 12 months
Quality of life	Survey	EQ-5D-5L (EuroQoL-5 dimensions)	6 weeks, 6 months, 12 months

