The resulting four time series will be inspected to identify secular trends and discontinuities/unexpected changes that might indicate a policy or regulatory action, or an external factor that might have affected opioid prescribing pattern. A timeline of opioid-related policy events affecting WA and/or OH (e.g., legislation, regulations, guidelines, large-scale interventions) will be constructed and overlaid on these time series to assess patterns and potential confounding related to the state-based environments. As part of Aim 3 (described below), qualitative methods will be used to understand the causes of unexplained fluctuations.

Finally, we will test whether implementation of the WA PA program (implemented in July 2013) or the OH RR program (implemented in March 2019) was associated with a statistically significant reduction in the rate of unsafe opioid prescribing using standard interrupted time series analysis (ITSA) techniques.^{1,2}

Aim 1. Analysis Topic B: Compare PA to RR with respect to unsafe opioid prescribing

This analysis is focused on the primary outcome for this study, unsafe opioid prescribing (defined earlier), using administrative data for the full WA and OH cohorts. We are planning for a one-year prospective timeframe, beginning July 2019 (based on dates of injury). Our cohort size estimates are 4,636 eligible workers in WA and 779 in OH .

Using WC claims and billing data from each state, we will track opioid prescribing for each injured worker for a full year after date of injury in order to test Hypothesis 1: Prospective PA with hard stops (WA) will be associated with statistically significantly less unsafe opioid prescribing compared to RR and prescriber notification (OH).

The primary outcome is the composite unsafe prescribing measure (i.e., meeting one or more of the 3 chronic-phase criteria in Table 1), modeled longitudinally over the three 3-month time windows, in order to assess the comparative effectiveness of PA/RR on the transition from early opioid therapy to longer-term unsafe opioid prescribing. Generalized estimating equations (GEE) panel models will be used to account for outcomes being measured during several time windows within individual patients.³

¹ Linden, A. (2015). Conducting interrupted time series analysis for single and multiple group comparisons. *The Stata Journal*, 15(2), 480-500.

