² Penfold, R. B., & Zhang, F. (2013). Use of interrupted time series analysis in evaluating health care quality improvements. *Acad Pediatr*, 13(6 Suppl), S38-44.

³ Aloisio, K. M., Swanson, S. A., Micali, N., Field, A., & Horton, N. J. (2014). Analysis of partially observed clustered data using generalized estimating equations and multiple imputation. *Stata J*, 14(4), 863-883.

The working correlation structure will be specified as exchangeable (this may be adjusted later in the Statistical Analysis Plan), and robust variance estimates will be used. (Though using the wrong correlation structure can be inefficient, GEE is not highly sensitive to using the wrong correlation structure, as long as there are at least 100 patient clusters and robust variance estimates are used—we expect to have over 3,000 patient clusters.)

The primary predictor is binary (1 for WA cases, 0 for OH cases). The GEE logit link function will be used to test the Aim 1 hypothesis, with unsafe opioid prescribing specified as a binary dependent variable in each time window. These regression models will provide an estimate of the odds of unsafe opioid prescribing in WA compared to OH, controlling for baseline differences in the two groups. The subacute phase measure, and also each individual component of the composite measure (i.e., chronic use, concurrent sedatives, high dose), will also be tested as distinct outcomes, which will provide information on potential variation in mechanisms and timing of ORP effect across WA and OH. Time will be included in the models (assigning an indicator for quarter since the date of injury; 0, 1, 2, 3), and interacted with state in order to assess (1) change in unsafe opioid prescribing over time and (2) differences in such change by state.

Covariates will be reassessed after more information is available regarding the availability, completeness, and cross-state comparability of various data fields in the OH data. Our initial plan is to include the following covariates for this analysis topic:

- Age
- Gender
- Pre-injury wage
- Marital status
- Number of dependent children
- Injury type
- Occupation
- Industry
- Rural/urban residence
- Provider type, specialty, and COHE or ECP affiliation
- Functional Comorbidity Index (FCI) and cancer diagnosis, based on WC billing data
- PDMP data, if available (see Analysis Topic D), will be used to control for opioid prescriptions in the 3 months prior to injury

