We are in the process of confirming the feasibility of obtaining PDMP data (and specifically the payer variable) from each state for the full WA/OH cohorts and all patients included in the survey sample. Presuming we are able to obtain the necessary PDMP data, the following analyses are planned.

We will construct the various unsafe opioid prescribing variables using PDMP data, using the same methods as used for WC billing data. Further, should the payer variable be available to us, we will construct two parallel sets of outcome measures using PDMP data: (1) using all PDMP prescriptions, regardless of payer; and (2) using only prescriptions with WC as the payer. (If the payer variable is unavailable, we will construct only the first measure.) Concordance of the outcome measures by data source (and potentially with and without payer restriction) will be assessed using Cohen's kappa.

Sensitivity of findings to the data source used for the unsafe opioid prescribing outcome measures will be assessed by using the alternate measures in hypothesis tests, as described under Analysis Topics B, C, and I.

Aim 1. Analysis Topic E: Frequency and outcomes of opioid review decisions

To the extent feasible, we will document the frequency of opioid review decisions and their outcomes (patients were or were not authorized to continue using opioids beyond the respective review periods) for each state. We are investigating the existence of these data and feasibility of obtaining them from

each state. This is planned as a simple descriptive analysis (counts and percentages).

Aim 1. Analysis Topic F: Subgroup response to opioid review decisions

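### Hypothesis 1 claims less unsafe opioid prescribing but is tested on WC billing, which the exposure can itself change; no rule ties the conclusion to the PDMP check or to its absence

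*Combined protocol and SAP*

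**What the plan says.** - **Claim.** Hypothesis 1 (section 2, repeated in section 7) predicts significantly less unsafe opioid prescribing in WA than in OH. It is not limited to prescriptions that WC pays for.
- **Data.** Section 6 says the outcome "will be measured as shown in Table 1 using pharmacy billing data from OH and WA, and validated using state PDMP data". Topic B, which tests Hypothesis 1, says "Using WC claims and billing data from each state, we will track opioid prescribing for each injured worker for a full year". The primary outcome is the chronic-phase composite at 3-6, 6-9 and 9-12 months.
- **WA exposure (section 5).** Here "payment for any opioid prescription billed beyond six weeks after the injury is denied unless the prescriber has submitted a checklist".
- **OH exposure (section 5).** The first record review is at 12 weeks. If best practices were not met, "cases are reviewed again at 16 weeks"; if they are still unmet, the prescriber "and worker are notified via letter that opioid coverage will end in 4 weeks".
- **PDMP check (Topic D).** "Presuming we are able to obtain the necessary PDMP data, the following analyses are planned": an all-payer outcome, a WC-payer-only outcome if the payer field is supplied, Cohen's kappa between sources, and repeat hypothesis tests with the alternate measures.
- **Related provisions.** Topic F explores switching to another prescriber or payer after coverage ends. Appendix A gives individual look-up as the OH fallback for PDMP retrieval.

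**The concern.** The WA exposure is a decision about WC payment, and the outcome is read from WC pharmacy billing. A worker who loses WC payment and fills the same prescription through cash or other insurance may still be receiving unsafe prescribing but is counted as not receiving it. Covariate adjustment and the common-support restriction cannot recover an outcome that was never recorded.

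Both programs can have this effect, but on different schedules, so capture may differ by state and by window. Only all-payer data can show whether it does, and the documents treat those data as not yet secured. If they are missing, following the plan would support a statement about unsafe prescribing that billing cannot establish. If they are obtained and disagree, nothing says which statement is made.

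**Working it through.** **1. Timing (section 5 and Table 1).** The WA payment rule starts at week 6, before all three primary windows. OH coverage can end from week 16 + 4 = 20. Taking 3-6 months as weeks 13 to 26, OH coverage can run for (20 − 13) × 7 = 49 days of that window and be absent for the other 6 of 13 weeks. The chronic-use component requires "≥60 days supply". Since 49 < 60, coverage ending at week 20 could remove that component in OH too, unless supply is counted by fill. Concurrent sedatives and high dose have no 60-day threshold. OH loss at 3-6 months therefore need not be zero.

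**2. Size of a possible bias.** The plan has no figure to reproduce: it gives no event rate, alpha or shifted share. The cohort sizes, 4,636 (WA) and 779 (OH), are from section 4. Everything else here is assumed: true all-payer risk 10% in both states in every window, two-sided 0.05, no covariates, and 30% of unsafe cases leaving WC billing everywhere except OH at 3-6 months.

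Billed risk = 0.10 × (1 − shift), averaged over three windows. WA: 0.07, odds 0.07/0.93 = 0.0753.

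| OH shift at 3-6 months | OH mean billed risk | Billed OR | False significant WA advantage |
|---|---|---|---|
| 0% | (0.10 + 0.07 + 0.07)/3 = 0.080 | 0.87 | about 22-32% |
| 15% | (0.085 + 0.07 + 0.07)/3 = 0.075 | 0.93 | about 9-11% |
| 30% (equal) | 0.070 | 1.00 | about 2.5% |
| 40% | (0.06 + 0.07 + 0.07)/3 = 0.0667 | 1.05 | about 1% |

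The last column comes from simulation with person-clustered variance and latent within-person correlation of 0.5 to 0.9, an approximation to the planned GEE. A hand check of the first row uses

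SE² = [1/(779 × 0.08 × 0.92) + 1/(4636 × 0.07 × 0.93)] × (1 + 2ρ)/3 = 0.0208 × (1 + 2ρ)/3,

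with ρ an assumed correlation of the billed outcomes. With ln 0.866 = −0.144:
- ρ = 0.3: SE 0.105, z = −1.37, chance Φ(−1.96 + 1.37) = 28%.
- ρ = 0.7: SE 0.129, z = −1.12, chance Φ(−1.96 + 1.12) = 20%.

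**3. The planned time interaction.** Topic B has time "interacted with state in order to assess (1) change in unsafe opioid prescribing over time and (2) differences in such change by state". Compare two cases, with OH at 10% throughout:
- True 30% WA reduction at 3-6 months only, no shifting: WA billed risks 0.07, 0.10, 0.10.
- No true effect, 30% WA shift at 3-6 months only: WA billed risks 0.07, 0.10, 0.10.

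The billed data have the same expected values, with a pooled OR of (0.09/0.91)/(0.10/0.90) = 0.89 in both. The interaction would reveal an early pattern but not its cause. All-payer data separate the cases: OR 0.89 in the first, 1.00 in the second.

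**4. Kappa.** Take all-payer risk of 10%, with billing missing 30% of it and adding no false positives. Observed agreement is 1 − 0.03 = 0.97. Chance agreement is 0.10 × 0.07 + 0.90 × 0.93 = 0.844. Kappa = (0.97 − 0.844)/(1 − 0.844) = 0.81. A kappa that looks reassuring can hide a 30% loss, and one pooled over states would not show whether the loss differs between them. The plan does not say whether kappa will be reported by state or window.

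**The case against.** The strongest reply is that the plan already covers this. Topic D builds the all-payer measure and repeats the tests, Topic F looks at other payers, Appendix A gives an OH fallback, and section 6 tells the reader that billing is the source. Section 7 calls the plan tentative. Most of this stands, and the plan deserves credit for it. What it does not supply is a rule linking the conclusion to the Topic D result, or to having no Topic D result.

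It is also fair that every size above is assumed, and that the largest depends on zero OH loss at 3-6 months, which step 1 gives reason to doubt.

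Three stronger readings are tempting, and the documents do not support them:
- *The billing comparison is biased toward WA.* No document gives a shifted share in either state. Equal shifting gives OR 1.00, and greater OH shifting reverses the bias.
- *PDMP should replace billing as the primary source.* PDMP linkage differs by state (vendor matching in WA, possibly name-and-birthdate look-up in OH). With no shifting and equal 10% risk, an OH look-up that missed 10% would give an all-payer OR of (0.10/0.90)/(0.09/0.91) = 1.12.
- *The claim should hinge on a test that the billing and all-payer ORs agree.* With a true 30% WA reduction, no shifting and the same linkage loss, billing gives 0.68 and all-payer 0.76. Both favor WA, but their ratio is 0.89. In simulation, a paired ratio test then let through only 0-1% of significant billing results. It let through 66-70% with equal shifting and that linkage loss, and 23-32% with perfect linkage and 0% OH shifting at 3-6 months.

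**Conclusion.** The point holds in a limited form. Hypothesis 1 is stated more broadly than its data source, the exposure can act on whether the outcome is recorded, and the one safeguard is conditional and carries no consequence for the claim. This rests on the text and not on the simulation. Whether any bias exists, and which way it runs, cannot be known from the documents. The figures of about 22-32%, 9-11% and 2.5% only show that unequal shifting could matter at these cohort sizes; they depend on the assumed 10% risk, 30% shift, 0.05 level and unadjusted pooled analysis. The plan should be amended on this point. The design and the primary data source need not change.

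**What to change.** Keep WC billing as the primary source.

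1. **Wording rule.** State the Topic B conclusion as WC-billed unsafe opioid prescribing. Extend it to unsafe prescribing overall only if PDMP data are obtained for both states and the all-payer estimate, shown with its confidence interval beside the billing estimate, supports the same conclusion. Set the rule before results by source are seen, and judge it on the all-payer estimate itself, not on a test of the billing/all-payer OR ratio. If PDMP data are missing in either state, the narrower wording stands.
2. **Reporting.** Give, by state and 3-month window, kappa and the share of all-payer unsafe windows that WC billing misses. Where payer is available, add the all-payer versus WC-payer-only contrast within PDMP, which helps separate payer shifting from linkage error.
3. **Minor.** State whether billed-but-denied lines count toward the outcome, with one rule for both states; the documents do not say.

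The cost is a few sentences and one table, since Topic D already builds the measures and reruns the tests. The downsides are a possibly narrower claim and reliance on an all-payer estimate that state-specific linkage error can bias. If the payer field is unavailable, shifting and linkage error cannot be separated, and the report should say so.

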Patient experience with opioid review procedures	Survey	Patient experience with opioid review procedures	6 months, 12 months
Perceived outcomes of insurer decisions from patient's perspective	Survey	Perceived outcomes of insurer decisions from patient's perspective	6 months, 12 months
Overall patient satisfaction	Survey	Overall patient satisfaction	6 weeks, 6 months, 12 months
Satisfaction with pain-related treatment	Survey	Satisfaction with pain-related treatment	6 weeks, 6 months, 12 months
Working full-time, part-time or not working	Survey	Working full-time, part-time or not working	6 weeks, 6 months, 12 months
Are wages more, less or about the same as before injury	Survey	Are wages more, less or about the same as before injury	6 weeks, 6 months, 12 months
Work status	WC claims data	Proxy: compensated time loss	6 weeks, 6 months, 12 months
Opioid poisoning events	WC billing data	ICD-10-CM codes	12 months

WC, workers' compensation.

Table 3. Exploratory/Other Outcome Measures

Title	Data Source	Description	Timeframe (after injury)
Opioid use disorder	Survey	TAPS (The Tobacco, Alcohol, Prescription medications, and other Substance Tool) – opiate pain reliever subset	12 months

7. Analytical Methods: Quantitative Analyses

Note: Because this is an observational study, and because we must submit this study protocol before Ohio data are made available, much of this plan is tentative. Updates will be made once more is known regarding the availability, completeness, and cross-state comparability of various data fields, data definitions, data generating processes, and procedures. A summary of the various planned analyses is provided in Table 4, followed by further detail regarding each analysis.

Table 4. Summary of Quantitative Data Analyses				
Aim	Analysis Topic	Analytic Approach	Outcome	Sample
1	A. Compare long-term prescribing patterns across states and identify discontinuities	Time series/ITSA	Any opioid prescription (acute) Unsafe opioid prescribing (subacute)	OH/WA 2010-2020
1	B. PA vs RR	GEE/propensity score & subgroup analysis	Unsafe opioid prescribing	OH/WA cohorts
1	C. PA vs RR	GEE/propensity score	Unsafe opioid prescribing	OH/WA survey samples
1	D. Prescribing data validation	Compare WC billing data with PDMP data	Unsafe opioid prescribing	OH/WA cohorts
1	E. Frequency/outcomes of opioid review decisions	Descriptives (N/percent that are/are not authorized)	Opioid review decisions	OH/WA cohorts

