Using PDMP data, we will explore whether patient subgroups within the WA and/or OH cohorts respond differently to review decisions ending opioid coverage (e.g., whether opioids were prescribed by a different prescriber or obtained using a different payment source). Patient subgroups of interest for this analysis topic include—but may not be limited to—patients on higher daily opioid doses, those taking opioids longer-term, those with back sprain, those still off work at 6 weeks, gender, age, etc. DEA numbers in PDMP data can be used to determine whether opioids were prescribed by a different provider following an opioid review decision ending opioid coverage. If the PDMP payer variable is available, we can also assess whether opioids were obtained using a non-WC payer following review decisions ending opioid coverage. Subgroups will be exploratory and may also be defined within the survey subset for this topic, so that subgroups constructed using baseline survey variables (e.g., pain level) can also be assessed.

Aim 1. Analysis Topic G: Describe usual care

We will describe usual care by measuring health care utilization indicators (e.g., timing and rates for hospitalization, physical therapy, imaging, surgery, etc.), using WC billing data for the full cohort in both states. Further, we will describe differences in such indicators between COHE and non-COHE patients in WA, and ECP and non-ECP patients in Ohio. Descriptive information about usual care will be stratified by injury type.

Aim 2

Specific aim 2. *Examine the comparative effectiveness of WA's PA program versus OH's RR program with regard to patient reported outcomes (pain, function, quality of life, return to work), harms (presence of opioid use disorder, opioid poisoning events) and work disability outcomes at 6 weeks, 6 months, and 12 months from date of injury.*

Hypothesis 2. *Prospective PA with hard stops (WA) will be associated with statistically significantly improved patient outcomes compared to RR and prescriber notification (OH). [See Analysis Topic H]*

Aim 2. Analysis Topic H: Compare PA to RR with respect to secondary outcomes

This analysis is focused on testing Hypothesis 2 (stated just above). Most secondary and exploratory patient outcomes will be based on survey data, but several will be based on WC data (see Tables 2 and 3).

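### Opioid poisoning is captured only through workers' compensation bills while the exposure is a workers' compensation payment rule, so capture may differ by state, in a direction that cannot be known in advance

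*Combined protocol and SAP*

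**What the plan says.** Aim 2 compares harms between the states and names two: opioid use disorder and opioid poisoning. The first is an exploratory survey measure (section 6, Table 3). The second, "Opioid poisoning events" in Table 2, comes from "WC billing data" by ICD-10-CM code over 12 months, and no second source is listed. It is therefore the only harm outcome taken from administrative data. Analysis Topic H tests Hypothesis 2 and notes that "Most secondary and exploratory patient outcomes will be based on survey data, but several will be based on WC data".

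Section 5 describes the two programs. In WA, "payment for any opioid prescription billed beyond six weeks after the injury is denied unless the prescriber has submitted a checklist". In OH, staff "review the medical record at 12 weeks to determine whether best practices were met". If they were not, the prescriber gets a letter and "cases are reviewed again at 16 weeks". If they are still unmet, the prescriber "and worker are notified via letter that opioid coverage will end in 4 weeks".

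Two other topics bear on this. Topic F explores, with prescription drug monitoring (PDMP) data, whether workers turn to another prescriber or payer after coverage ends. Topic D builds alternate, partly payer-neutral measures of unsafe prescribing, and sensitivity to data source is "assessed by using the alternate measures in hypothesis tests, as described under Analysis Topics B, C, and I". Topic H is not on that list.

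**The concern.** A poisoning enters the data only if its emergency or hospital bill goes to WC. That seems likely while WC is paying for the opioid. It may be less likely once the worker pays cash or uses another insurer. A poisoning that WC never paid for is not a missing value that the Missing Data section would catch; the worker is simply counted as event-free for 12 months.

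Since the programs differ in when WC payment can stop, the exposure could affect whether the harm is seen as well as whether it occurs. Topic H could then report fewer poisonings in WA, or no excess, when true harm is equal or higher. The plan sees the dependence on payer for prescribing (Topics D and F) but gives the harm outcome no matching check.

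**Working it through.** The plan gives no poisoning rate, capture probability or power for this outcome, so there is no stated figure to reproduce. The steps below show what the timing rules could do under stated assumptions.

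**Inputs from the documents.** WA stop at week 6 if no checklist is filed; OH second review at week 16 and 4 weeks' notice (section 5). Window of 12 months, taken as 52 weeks (Table 2). Baseline survey samples of 3,120 in WA and 525 in OH (Topic H).

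**Assumptions.** OH's weeks run from injury. The true poisoning rate is equal in both states and constant over 52 weeks. Capture is complete while WC covers opioids and has probability *c* afterwards. A share *f* of true poisonings arises in workers whose coverage is ended. The documents give neither *c* nor *f*.

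**Step 1, timing.** OH stop = 16 + 4 = week 20. Gap = 20 − 6 = 14 weeks. Weeks remaining after the stop: 52 − 6 = 46 in WA and 52 − 20 = 32 in OH. The earlier OH review points are 6 weeks (12 − 6) and 10 weeks (16 − 6) after WA's stop, but neither ends coverage.

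**Step 2, capture in stopped workers.** WA = (6 + 46*c*)/52; OH = (20 + 32*c*)/52.

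| *c* | WA captured | OH captured | apparent WA/OH ratio |
|---|---|---|---|
| 0 | 12% | 38% | 0.30 |
| 0.25 | 34% | 54% | 0.63 |
| 0.5 | 56% | 69% | 0.81 |
| 0.75 | 78% | 85% | 0.92 |
| 1 | 100% | 100% | 1.00 |

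**Step 3, dilution.** If only a share *f* of events arises in stopped workers, capture in each state is (1 − *f*) + *f* × (Step 2 value). With the same *f* in both states:

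| *f* | *c* = 0 | *c* = 0.25 | *c* = 0.5 | *c* = 0.75 | *c* = 1 |
|---|---|---|---|---|---|
| 0.5 | 0.81 | 0.87 | 0.92 | 0.96 | 1.00 |
| 0.25 | 0.92 | 0.94 | 0.96 | 0.98 | 1.00 |
| 0.1 | 0.97 | 0.98 | 0.99 | 0.99 | 1.00 |

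**Step 4, unequal shares.** Capture can be rewritten as 1 − *f*(46/52)(1 − *c*) in WA and 1 − *f*(32/52)(1 − *c*) in OH, each with its own *f*. For any *c* below 1 the ratio is below 1 only if 46*f*(WA) exceeds 32*f*(OH). The direction reverses once OH's share is more than 46/32 = 1.44 times WA's. At *c* = 0.5:

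- WA 50%, OH 10%: 0.779/0.969 = 0.80
- WA 25%, OH 50%: 0.889/0.846 = 1.05
- WA 10%, OH 50%: 0.956/0.846 = 1.13

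**Step 5, precision.** At an assumed poisoning rate of 0.1% to 1%, the baseline survey samples would yield 3,120 × 0.001 to 3,120 × 0.01 = about 3 to 31 events in WA, and 525 × 0.001 to 525 × 0.01 = about 0.5 to 5 in OH. At 1%, the 95% interval for the ratio extends by a factor of exp(1.96 × √(1/31.2 + 1/5.25)) = 2.5 each way.

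**The case against.** The strongest reply is that the mechanism is not in the documents. Both programs govern payment for opioid prescriptions, not for emergency or hospital care. Nothing says that poisoning care leaves WC billing when opioid payment stops; if it does not, *c* = 1 and there is no bias. This stands, and it is why the point is conditional.

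A reader might also infer that WA's program ends coverage 14 weeks earlier for the cohort as a whole. It does not: WA keeps paying if the checklist is filed, and OH stops only after two unmet reviews. The 14 weeks compares only workers who are refused in each state, and those shares are unknown. Topic E would count review decisions if the data can be obtained.

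The plan is not silent on nearby matters. Topic F looks for non-WC opioids after a stop, section 7 promises updates on cross-state comparability, the Missing Data section allows sensitivity analyses where indicated, and the survey measure of opioid use disorder does not depend on payer. But Topic F and the PDMP concern prescriptions, the general promises name no step for poisoning, and opioid use disorder is a different harm.

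Finally, events will be few, so the comparison is imprecise in any case. That lowers the weight of the outcome, but a wide interval does not correct unequal capture, and a low WA count could still be read as reassurance.

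**Conclusion.** The concern holds in conditional form. Poisoning is seen only through WC bills, the exposure is a rule about WC payment, and no planned analysis tests whether capture differs by state. Under the assumptions above, with equal shares, the spurious ratio runs from 0.30, which needs no capture after the stop and every event in stopped workers, to 1.00. If a quarter or fewer of the events arise in such workers, it stays between 0.92 and 1.00.

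A reader might go further and infer that the bias favours prior authorization. The documents do not support that. The sign depends on the share stopped in each state, and WA's checklist route makes a smaller WA share quite possible; above the 1.44-fold threshold the bias runs against WA. Neither size nor direction is established. What follows is that a WA–OH difference in this outcome, or its absence, cannot be read as a difference in poisoning without an explicit allowance for capture. For a secondary outcome with a cheap remedy, this should be changed but does not threaten the primary analysis.

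**What to change.** 1. In Table 2 and Topic H, name the outcome *WC-billed opioid poisoning*. State that a lower or equal WA count will not by itself be taken as lower or equal poisoning, or as support for Hypothesis 2. Report an observed WA excess with the same caveat; do not suppress it.

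2. Add a tipping-point table to Topic H that varies the capture probability after coverage ends and the share stopped in each state, and shows where the WA–OH difference disappears or reverses. Topic E could inform the shares if its data arrive. It would count workers, so using those counts as shares of events needs the further assumption that the poisoning rate is the same in stopped and other workers.

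3. If the PDMP payer field becomes available, show beside that table, by state, the share of opioid days after week 6 that WC did not pay for. Topic D already plans measures with and without the payer restriction, so this is a small addition.

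A rate per month of active WC billing is not a good substitute. A poisoning bill itself makes its month active, the program can affect billing activity, and a worker with other WC bills who buys opioids with cash would still count as event-free. Billing-active time by state can be reported descriptively at most.

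The cost is SAP wording, one extra table and a narrower harm claim. Items 1 and 2 need no new data.
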